**LIST OF ABBREVIATIONS**

AE	adverse event
CFR	Code of Federal Regulations
CRF	case report form
CTRA	conserved transcriptional response to adversity
DMC	Data Monitoring Committee
DSMB	Data Safety Monitoring Board
FDA	Food and Drug Administration
GCP	Good Clinical Practice
HIPAA	Health Insurance Portability and Accountability Act of 1996
ICF	informed consent form
ICH	International Conference on Harmonisation
IEC	Independent Ethics Committee
IRB	Institutional Review Board
MA	methamphetamine
MSM	men who have sex with men
MUD	methamphetamine use disorder
PI	Principal Investigator
SAE	serious adverse experience
SCID-5	The Structured Clinical Interview for DSM-5
VL	viral load

**PROTOCOL SYNOPSIS**

TITLE	Expression of stress markers in MSM living with HIV receiving contingency management for methamphetamine use disorder (a.k.a. “EXPRESS+”)
SPONSOR	[name], MPH
FUNDING ORGANIZATION	
NUMBER OF SITES	1
RATIONALE	Determining whether a patient is both feeling better and improving physiologically when treating people living with HIV (PLWH) for methamphetamine use disorder requires identification of a clinically significant measure separate from abstinence. This study will to address this challenge by testing a gene expression (mRNA) pattern identified by the field of social genomics, which may provide insight into both psychosocial health and biological processes that impact chronic disease risk in PLWH receiving MUD treatment.
STUDY DESIGN	This is a within-subjects, two-arm clinical trial with 35 HIV-positive MSM receiving contingency management for treatment of methamphetamine use disorder and 20 HIV-positive MSM serving as a non-substance-using healthy control (N=55 total).
PRIMARY OBJECTIVE	To investigate whether differences in CTRA expression (mRNA) coincide with differences in methamphetamine use and viral load over the course of 12 weeks in HIV-positive MSM with and without methamphetamine use disorder.

SECONDARY OBJECTIVES
	
 
• To investigate whether differences in seven psychosocial dimensions of drug addiction (Short Inventory of Problems Revised (SIP-R))—physical, social, intrapersonal, interpersonal, impulse control—are associated with differences in CTRA gene expression.
 
• To conduct an exploratory pilot investigation to determine the degree to which CTRA mediates the association between METH use and viral suppression.
 

NUMBER OF SUBJECTS
	55

SUBJECT SELECTION CRITERIA
	
Inclusion Criteria
 
HIV-positive MSM with MUD in the contingency management condition (N = 35)
 
 
1. Assigned male sex at birth
 
2. 18 to 45 years of age
 
3. Reports having sex with men in the past 12 months.
 
4. HIV-positive (confirmed by certification or by HIV rapid test)
 
5. Has an HIV care provider (last seen in the past 12 months)
 
6. Has a current antiretroviral prescription
 
7. Meets the DSM-5 criteria for MUD using SCID-5
 
8. Urine test is positive for MA within 30 days of their screening visit
 
9. Seeking treatment for MUD.
 
10. Ability to attend twice weekly appointments for drug testing and treatment
 
 
HIV-positive MSM non-substance-using control (N = 20)
 
 
1. Assigned male sex at birth
 
2. 18 to 45 years of age
 
3. Reports having sex with men in the past 12 months.
 
4. HIV-positive (confirmed by certification or by HIV rapid test)
 
5. Has an HIV care provider (last seen in the past 12 months)
 

	
6. Has a current antiretroviral prescription
 
Exclusion Criteria
 
HIV-positive MSM with MUD in the contingency management condition (N = 35)
 
 
1. Identifies as (cis- or transgender) female
 
2. Reports another current or past substance use disorder
 
3. Reports being in another intervention or clinical trial for substance use
 
4. Positive test for opioids, cocaine, and/or MDMA
 
 
HIV-positive MSM non-substance-using control (N = 20)
 
 
1. Identifies as (cis- or transgender) female
 
2. Positive test for MA, opioids, cocaine, and/or MDMA.
 
3. Reports substance use (MA, opioids, cocaine, MDMA, hallucinogens, heavy alcohol use, and/or tobacco) in the past 6 months
 
4. Reports past or current substance use disorder
 

BEHAVIORAL INTERVENTION	
Those with MUD (MA+/HIV+) will receive contingency management, a positive reinforcement behavioral treatment with escalating rewards for consecutive negative urine tests, capped at a maximum of \$30 per negative result.

CONTROL GROUP	
Those in the non-substance-using control condition (MA-/HIV+) will only not receive an intervention. They will only attend four appointments total after their screening to provide blood draws, urine samples, and complete their behavioral surveys.

DURATION OF SUBJECT PARTICIPATION AND DURATION OF STUDY	
Each subject will be on study for up to 17 weeks
 
Screening period: 1-4 weeks
 
Baseline assessment: 1 week
 
Treatment: 8 weeks
 
Follow-up: 4 weeks after end of treatment
 
The total duration of the study is expected to be 4 years. 1 year of rolling subject recruitment, 1 year for final subject follow-up, 1 year of biospecimen processing, and 1 year of analysis.

CONCOMITANT MEDICATIONS	NONE
EFFICACY EVALUATIONS	
PRIMARY ENDPOINT	
 
• A gene expression (mRNA) pattern called the conserved transcriptional response to adversity (CTRA) will be measured using transcriptome profiling of leukocytes.
 

SECONDARY ENDPOINTS	
 
• Negative urine tests for methamphetamine
 
• HIV viral load from plasma
 

OTHER EVALUATIONS	
 
• Plasma concentration of methamphetamine
 
• Short Inventory of Problems Revised (SIP-R)
 
• Sociodemographics – age, race, education level, sexual orientation, housing status, body mass index (BMI), smoking history, and heavy alcohol use history
 

SAFETY EVALUATIONS	
 
• MA use frequency based on urine tests
 
• HIV viral load
 
• Incidence of adverse events
 

PLANNED INTERIM ANALYSES	This will be an NIH-funded study through the K01 mechanism. We have just received requested for Just In Time. When approximately

	50% of patients have completed the study through Week 4, an interim analysis for safety will be conducted when 25% of participants complete Week 4. Serious adverse events will be monitored by the investigators on an ongoing basis throughout the study.
STATISTICS	
Primary Analysis Plan	Using a linear mixed effects regression, we will test whether a negative MA urine test is associated with reductions in CTRA contrast scores across four time points—Visits B, 4.2 (Week 4), 8.2 (Week 8), and 12.0 (Week 12 follow-up). We will use a time (days) by MA urine result interaction term to estimate difference in change in CTRA as a function of MA test result. Using a mixed effects logistic regression, we will test whether CTRA expression is associated with viral suppression (<200c/mL) across three time points— Visits B, 4.2 (Week 4), 8.2 (Week 8), and 12.0 (Week 12 follow-up). We will include a time (days) by CTRA expression interaction term to test this association longitudinally.
Rationale for Number of Subjects	Power analysis for this pilot study indicates that a minimum of 135 person-observations will be sufficient to test whether MA use or the psychosocial Short Inventory of Problems (SIP-R) are associated with CTRA expression, assuming a medium effect size of 0.15 and power level of .80. Additionally, a logistic model testing whether CTRA is associated with viral suppression would require a minimum of 154 person-observations, assuming a power level of .80, a CTRA standard deviation of 1.44, mean centering of CTRA, and an odds ratio of 1.5. When modeling viral load as a continuous outcome, 135 person-observations is the minimum to test whether CTRA is associated with viral load (c/mL), assuming a medium effect size of 0.15 and power level of .80. These analyses will include 55 participants over four measurements of CTRA, for a total of 220 person-observations (176 person-observations at 80% retention), which is sufficient for these thresholds.

## 1 BACKGROUND

Contingency management (CM), which provides incentives that escalate in value for provision of consecutive biomarkers demonstrating drug abstinence, is an effective positive reinforcement approach to promoting abstinence from methamphetamine (MA) and other substances.

### 1.1 Treatment of methamphetamine use disorder and management of HIV

Use of MA is disproportionately higher among men who have sex with men (MSM) than the general U.S. population (5.9% in HIV-negative MSM and 12.3% in HIV-positive MSM) (1, 2). Chronic MA use is linked to myriad health conditions including psychiatric disorders, cardiovascular disease, social problems, and infectious diseases such as HIV (25). MA use reduces adherence to antiretroviral therapy (ART) and engagement in HIV care (3, 4), and induces immune dysfunction (5). All of these factors can hamper people living with HIV (PLWH) from achieving and sustaining viral suppression, which contributes to forward HIV transmission. Reducing MA use is essential to managing HIV, reducing transmission, and maintaining health in PLWH with MA use disorder (MUD).

There are no effective pharmacological treatments in place for MUD (40). The most robust treatments use behavioral approaches (41-43). Research in substance use intervention has demonstrated that contingency management (CM), which provides incentives that escalate in value for provision of consecutive biomarkers demonstrating drug abstinence, is an effective positive reinforcement approach to promoting abstinence from MA and other substances (6, 43-49). CM is based on the theory that MUD or other substance disorder is due to sustained, high-value drug reinforcement and that providing incentives that compete with drug reinforcement can successfully alter drug taking and produce sustained drug abstinence (15).

### 1.2 A social transcriptomics perspective on MA treatment and HIV

With support from this K01, I will conduct a pilot investigation to determine whether a neurally regulated “stress” gene expression profile (mRNA) observable in circulating blood cells can serve as a clinically meaningful, non-abstinence-based endpoint for contingency management (CM) for MA use disorder (MUD) in MSM living with HIV. Ensuring that a patient is both feeling better and improving physiologically are fundamental tasks to addiction treatment, yet abstinence alone—based on urine tests—has been the standard clinical outcome for MA treatment (7, 32, 33). However, this outcome is incomplete, especially when seeking to determine whether treatment improved psychosocial health and attenuated the adverse biological processes linking drug use to chronic disease (33). Both of these aspects of health are important to understanding substance use treatment efficacy. Promoting psychosocial health and reducing

distress may be important to long-term recovery from MUD, especially for PLWH with MUD (6, 7). Assessing biological patterns linked to MA use and pathogenesis may help in identifying individuals at particularly high risk for severe addiction and for development of MA-related chronic disease (8, 9). Moreover, the lack of a currently accepted clinical endpoint beyond abstinence may be limiting the number of approved therapies for MUD, yet identification of such an endpoint remains a challenge for researchers (32, 33).

I propose to assess a gene expression (mRNA) pattern called the conserved transcriptional response to adversity (CTRA), which may provide insight into changes in both psychosocial health and pathogenesis over the course of MA treatment. According to the field of social genomics, the CTRA is an intracellular pattern is marked by upregulated expression of pro-inflammatory genes (i.e., increases in mRNA) and downregulated expression of Type I interferon (IFN-I) and antibody-synthesis genes (i.e., decreases in mRNA) (9, 11-14) in response to negative psychosocial experiences such as emotional distress, isolation, and rejection, as well as compulsive and addictive behaviors (9, 11-14) (see Table 1). In contrast, experiences of eudaimonic well-being and sense of purpose and meaning are associated with low CTRA levels (15, 16). The CTRA is mediated by neurally-induced upregulation of inflammatory transcription factor activity (cAMP response element binding protein (CREB), nuclear factor kappa B (NF- $\kappa$ B), and activator protein 1 (AP-1)), and downregulated activity of interferon responsive transcription factors (IRF), which proximally induce these empirical differences in gene expression. As such, the CTRA profile can be assessed either by quantifying the activity of pre-specified sets of inflammatory and interferon-related genes (i.e., mRNA transcripts), or by bioinformatic measures of transcription factor activation derived from genome-wide transcriptional profiling.

It is important to note that although CTRA measurement involves the use of basic science techniques, its application largely lies in behavioral and psychosocial sciences that aim to expand understanding of the stress-disease relationship (9). Evaluation of this CTRA profile with MA addiction treatment outcomes represents a significant advancement and offers the opportunity to describe health enhancements from treatment beyond that offered solely by behavioral markers of abstinence.

Many of the psychosocial problems that are comorbid with MA use are associated with CTRA expression. Socioeconomic challenges, discrimination, childhood trauma, and interpersonal conflict are associated with chronic MA use in MSM (34, 50-56) and are known drivers of CTRA expression (12, 14, 57-60). My pilot research has shown three-fold elevations

[figure not shown]

Figure 1. CTRA expression in HIV-negative MSM who experienced homophobic victimization (10)

in CTRA expression in HIV-negative MSM who experienced homophobic victimization (Figure 1) (10), a problem also comorbid with MA use in MSM (34). The CTRA has also been shown to be related to the development of depressive and

Table 1. CTRA gene expression and transcription factor activation in response to stress vs. well-being

Stress response	Well-being response	Transcription factor	Genes expressed
↑	↓	CREB, NF-κB, AP-1	Inflammatory: IL1A, IL1B, IL6, IL8, TNF, PTGS1, PTGS2, FOS, FOSB, FOSL1, FOSL2, JUN, JUNB, JUND, NFKB1, NFKB2, REL, RELA, and RELB
↓	↑	IRF	Interferon: GBP1, IFI16, IFI27, IFI27L1-2, IFI30, IFI35, IFI44, IFI44L, IFI6, IFIH1, IFIT1-3, IFIT5, IFIT1L, IFITM1-3, IFITM4P, IFITM5, IFNB1, IRF2, IRF7-8, MX1-2, OAS1-3, and OASL Antibody synthesis: IGH, IGLL1, and IGLL3

anxiety-related disorders (18-22), which are highly comorbid with MA use (23-25). Research on compulsive gaming also may suggest that CTRA is linked to addictive behaviors and dynamics (16). Participants who experienced internet gaming as compulsive

, isolating, or dissatisfying had increases in their CTRA gene expression, while those who felt accomplishment and connectedness with online gamers had low CTRA levels (16).

The CTRA also involves some of same gene regulatory pathways that contribute to MA-related pathogenesis, such as those involving inflammation and innate antiviral responses (particularly relevant to PLWH). Chronic MA use in pre-clinical experiments and stimulation of inflammation using lipopolysaccharide (LPS) was shown to induce anxiety-like and sickness behaviors in adult rats, while neonatal exposure to LPS-induced inflammation was linked to behavioral sensitization to MA self-administration during adulthood (23, 24, 61, 62). Chronic MA use is also associated with increased CREB, AP-1, and NF-κB activation, transcription factors driving CTRA gene expression and likely involved in MA-induced inflammation (8, 28-31). The CTRA has also been epidemiologically linked to inflammatory health problems such as cardiovascular disease (26, 27), a common cause of mortality in people with MUD (63, 64).

Both chronic MA use and comorbid psychosocial problems such as HIV stigma and depression have been linked to the progression of HIV (65-67). One explanation for this may be their impact on poorer ART adherence (68), while another possibility is the mediating role of inflammation and/or impaired antiviral response on viremia (67, 69-73). Prior research has demonstrated that greater cytokine levels and activation of CTRA-related transcription factors such as NF-κB and CREB induce replication of HIV and predict increases in viral load (30, 74-77). Conversely, HIV itself induces chronic inflammation and enhances risk of inflammatory-related health conditions such as cardiovascular disease (78-80) and depression (81). Risk of these inflammatory conditions in PLWH is further exacerbated by comorbid MA use (69, 70).

For these reasons, measuring inflammatory patterns in CTRA may have clinical relevance to management of HIV and related chronic conditions in the context of MA treatment.

However, the impact of IFN-I activity on HIV disease progression is less clear (82, 83). While IFN-I responses to acute HIV are involved in initial reduction of the virus (71, 72), prolonged IFN-1 activation can lead to immune dysregulation and T-cell exhaustion, and in turn, increased viral load (82, 83). As stated previously, CTRA gene expression involves threat/stress-induced increases in inflammatory gene expression and decreases in IFN-1 and antibody gene expression, all of which are markers linked to HIV viral load. Whether physiologic patterns of IFN gene expression underlie the link between psychosocial health and the body's management of HIV warrants investigation.

## 2 STUDY RATIONALE

There is a need for a biomarker measure than can serve as a clinically meaningful, non-abstinence-based endpoint for contingency management (CM) for MA reduction in HIV-positive MSM with MA use disorder. MA use disorder is frequently comorbid with HIV infection in MSM, and adversely impacts management of HIV. Abstinence determined by urine testing has been the only standard clinical outcome for MA treatment, but provides an incomplete picture of patient recovery. The potential benefit of measuring the CTRA as a biomarker outcome linked to MA abstinence is that this measure may provide insight into both psychosocial health and biological patterns of pathogenesis as MSM living with HIV change their MA use. While MA abstinence is currently the primary outcome for treatment, the CTRA is a valid measure of both biological and psychosocial aspects of health, both of which are important to documenting substance use treatment efficacy. Promoting psychosocial health and reducing distress may be important to long-term recovery from MA use disorder, especially in PLWH (6, 7). Moreover, assessing biological patterns linked to MA use and pathogenesis may help in identifying individuals at particularly high risk for addiction and for development of MA-related chronic disease (8, 9).

Despite the CTRA's scope and nature, CTRA measurement should not be a substitute for directly asking MA-dependent patients how they are feeling/functioning. Rather, CTRA measurement should complement psychosocial self-reports and urine tests in substance use research, because it may help to identify patients who require additional intervention beyond the any single treatment approach (7, 32, 33). Assessing CTRA may also offset inaccuracies in self-report measures caused by limited recall, social desirability bias, power of suggestion, or other misconceptions (9, 32). Methods used to measure CTRA are accessible using common technologies like those used to quantify HIV viral load. Findings from my proposed research

may offer a framework to apply CTSA assessment to the treatment of more generalized populations affected by MUD, or for assessing outcomes in people receiving treatment for other substances such as opioids or other stimulants. Outside of addiction, CTSA assessment may also provide insight into stress-biology processes connecting HIV stigma, mental health problems, and chronic disease, challenges that to extend to broader communities of PLWH (84-86).

## 2.1 Risk / Benefit Assessment

### Risks

Contingency management. Some clinicians may deem the use of monetary incentives to be too tempting for some patients to receive money, who may then go out and purchase drugs. This risk is mitigated by the lack of earnings from not being able to provide a urine sample negative for drug metabolite. That said, all participants are aware that they must abstain for the entire period of 8 weeks to earn the maximum amount, which can then be used to buy consumptive goods such as food, other essential items for their families, or hedonistic goods, such as tickets to movie theaters, to meals at restaurants or for other recreational activities. Most people with MUD seek treatment to improve their lives, for themselves and for their families, and so we will help to incentivize the money to be spent on life-improving factors as opposed to drugs. There is also risk that participants with MUD will not improve or possibly worsen during CM participation. Participants will receive referrals to additional services if they require further care following the study, and the PI ([name]) will discuss participant follow-up care as needed (see Data and Safety Monitoring Plan).

Blood Draws. The risks of the blood draws include pain, lightheadedness, fainting, and on rare occasions, infection. Possible bruising at the site of the needle puncture may also occur, and it will heal and disappear within days (several weeks at most.) Rarely, the vein may clot. The risk and discomfort are slight. Good venipuncture practices reduce the pain and likelihood of bruising and secondary infection. Precautions will be taken with participants who have a history of fainting during blood draws, such as having the patient lie down during the procedure.

Urine testing for substance misuse. There are minimal risks to urine testing that include embarrassment or emotional discomfort following positive urine test results.

Survey assessments. There is minor risk that completion of survey assessments may induce distress. Social consequences of research participation. The PI, [name], and the study site will make every effort to protect participant's privacy and confidentiality. However, it is possible that involvement in the study could become known to others, and that social harms may result such as unfair or discriminatory treatment from the participant's social network. All guidelines for the protection of Personal Health Identifiers will be followed.

### Protection against risks

There is minor risk that completion of survey assessments may induce distress. In such instances, participants will meet with study staff members for debriefing. The PI, [name], will keep a record of the number and type of cases that require invoking a rescue protocol and discuss these with the Medical Director, [name] and mentor [name] for participant follow-up. [name] is a licensed psychologist and will be on call in the rare case that mental health intervention is required.

There is a risk that some participants may have a MA addiction that is too severe to be adequately treated on an outpatient basis or that for any reason does not respond to the CM program. At all points during the trial participants have access to treatment facilities instead of or in addition to the CM program. Those who wish to focus solely on treatment and not on research can withdraw from study participation at any time. Any unexpected events that arise during specimen collection, survey administration, or the contingency management program that caused harm and/or that affects the risk to all participants in the research will be reported on an annual basis to the IRB.

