### 11.2.1 Serious Adverse Experience Reporting

Study sites will document all SAEs that occur (whether or not related to study drug) per UCLA OHRPP Guidelines. The collection period for all SAEs will begin after informed consent is obtained and end after procedures for the final study visit have been completed.

In accordance with the standard operating procedures and policies of the local Institutional Review Board (IRB)/Independent Ethics Committee (IEC), the site investigator will report SAEs to the IRB/IEC.

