## 14 DATA SAFETY MONITORING

A data and safety monitoring plan (DSMP) will be used to monitor good clinical research procedures regarding data and safety of participants. During data collection, the Principal Investigator ([name]), and key personnel will monitor the practical aspects of the project to ensure that participants and the data are being protected, especially in conducting quality assurance of all informed consent documents in real time. All standard safety procedures and ethical practices will be adhered to per the IRB of the University of California, Los Angeles (UCLA) (a.k.a., Office of the Human Research Protection Program (OHRPP)), and will use secure, HIPAA-compliant technology per UCLA Health Sciences information and technology (DGIT) standards. [name] and key personnel will communicate regularly with UCLA OHRPP for coordinated review of ethical practices, safety procedures, and adherence to confidentiality/privacy agreements.

[name] will prepare administrative reports every month or more frequently as requested describing study progress including the following to review with primary mentor, [name], and co-mentor [name]:

- Actual versus expected enrollment figures
- Demographic and clinical characteristics
- Missing visits and case report forms
- Number and type of clinically significant/adverse events (CSEs), AEs and UPs
- Randomly audited consent forms of five participants to determine whether they are available and properly executed.
- Aggregate values of clinical laboratory results

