### **17.2 Institutional Review Boards and Independent Ethics Committees**

The protocol and consent form will be reviewed and approved by the IRB/IEC of each participating center prior to study initiation. Serious adverse experiences regardless of causality will be reported to the IRB/IEC in accordance with the standard operating procedures and policies of the IRB/IEC, and the Investigator will keep the IRB/IEC informed as to the progress of the study. The Investigator will obtain assurance of IRB/IEC compliance with regulations.

Any documents that the IRB/IEC may need to fulfill its responsibilities (such as protocol, protocol amendments, Investigator's Brochure, consent forms, information concerning patient recruitment, payment or compensation procedures, or other pertinent information) will be submitted to the IRB/IEC. The IRB/IECs written unconditional approval of the study protocol and the informed consent form will be in the possession of the Investigator before the study is initiated. The IRB/IECs unconditional approval statement will be transmitted by the Investigator to the Sponsor or designee prior to the shipment of study supplies to the site. This approval must refer to the study by exact protocol title and number and should identify the documents reviewed and the date of review.

Protocol and/or informed consent modifications or changes may not be initiated without prior written IRB/IEC approval except when necessary to eliminate immediate hazards to the patients or when the change(s) involves only logistical or administrative aspects of the study. Such modifications will be submitted to the IRB/IEC and written verification that the modification was submitted and subsequently approved should be obtained.

The IRB/IEC must be informed of revisions to other documents originally submitted for review; serious and/or unexpected adverse experiences occurring during the study in accordance with the standard operating procedures and policies of the IRB; new information that may affect adversely the safety of the patients of the conduct of the study; an annual update and/or request for re-approval; and when the study has been completed.

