### **17.5 Investigator Responsibilities**

By signing the Agreement of Investigator form, the Investigator agrees to:

1. Conduct the study in accordance with the protocol and only make changes after notifying the Sponsor (or designee), except when to protect the safety, rights or welfare of subjects.
2. Personally conduct or supervise the study (or investigation).
3. Ensure that the requirements relating to obtaining informed consent and IRB review and approval meet federal guidelines, as stated in § 21 CFR, parts 50 and 56.
4. Report to the Sponsor or designee any AEs that occur in the course of the study, in accordance with §21 CFR 312.64.
5. Ensure that all associates, colleagues and employees assisting in the conduct of the study are informed about their obligations in meeting the above commitments.
6. Maintain adequate and accurate records in accordance with §21 CFR 312.62 and to make those records available for inspection with the Sponsor (or designee).
7. Ensure that an IRB that complies with the requirements of §21 CFR part 56 will be responsible for initial and continuing review and approval of the clinical study.
8. Promptly report to the IRB and the Sponsor (or designee) all changes in the research activity and all unanticipated problems involving risks to subjects or others (to include amendments and IND safety reports).
9. Seek IRB approval before any changes are made in the research study, except when necessary to eliminate hazards to the patients/subjects.
10. Comply with all other requirements regarding the obligations of clinical investigators and all other pertinent requirements listed in § 21 CFR part 312.

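### Section 2.1 puts unexpected harmful or risk-changing events on annual IRB reporting, which conflicts with sections 17.5 and 17.2, and no provision says which rule prevails

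*Combined protocol and SAP*

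**What the plan says.** Five places in the combined protocol and SAP bear on when the IRB, or anyone else, learns of an unexpected event.

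- **Section 2.1, Protection against risks.** Unexpected events arising in specimen collection, surveys or contingency management that did harm, or that alter the risk for every participant, "will be reported on an annual basis to the IRB".
- **Section 17.5, item 8.** The investigator agrees to: "Promptly report to the IRB and the Sponsor (or designee) all changes in the research activity and all unanticipated problems involving risks to subjects". The item extends to risks to others as well. It gives no number of days.
- **Section 17.2.** The IRB must be informed of "serious and/or unexpected adverse experiences occurring during the study in accordance with the standard operating procedures and policies of the IRB". The same list names an annual update or request for re-approval as a separate item. An earlier paragraph of 17.2 also requires serious adverse experiences to go to the IRB whatever their cause.
- **Section 11.2.1.** Under the local IRB's procedures and policies, "the site investigator will report SAEs to the IRB/IEC". No interval is given.
- **Section 14.** The principal investigator "will prepare administrative reports every month or more frequently as requested", for review with the mentors. Listed contents include "Number and type of clinically significant/adverse events (CSEs), AEs and UPs". The section also provides for regular contact with the UCLA human research protection office (OHRPP), which it equates with the UCLA IRB.

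None of these provisions limits the annual rule in 2.1 to minor events, refers it to another section, or says which rule takes precedence.

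**The concern.** Section 2.1 is the only provision that names the study's own activities and attaches a reporting interval to events arising from them. Section 17.5 is a general list of investigator responsibilities. Site staff looking for the study-specific rule could reasonably stop at 2.1 and hold an event for the annual report, although 17.5 calls for prompt reporting.

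What is at stake is the IRB's chance to act on a newly recognised risk while participants are still exposed to it. Individual participation is short and recruitment is planned to last one year, so an annual cycle is long compared with the time in which a change to procedures or consent could help those enrolled.

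**Working it through.** The plan gives no statistical figure to reproduce. The check is a comparison of texts plus a simple timing calculation.

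**Step 1. Provisions side by side.**

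| Section | Events covered | Recipient | Timing |
|---|---|---|---|
| 2.1 | Unexpected, study-related, caused harm or affects risk to all | IRB | Annual |
| 17.5 item 8 | Unanticipated problems involving risk | IRB and sponsor | Prompt, no day count |
| 17.2 | Serious and/or unexpected adverse experiences | IRB | IRB procedures, no interval stated |
| 17.2 | Annual update or re-approval request | IRB | Annual |
| 11.2.1 | Serious adverse events | IRB | IRB procedures, no interval stated |
| 14 | Adverse events and unanticipated problems | Mentors | At least monthly |

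**Step 2. Do the event sets overlap?** An unexpected event that alters the risk to every participant is, on ordinary wording, an unanticipated problem involving risk. An unexpected event that caused harm will often be one too, and it is likely to be an unexpected adverse experience under 17.2. The protocol does not define unanticipated problems, so overlap is established but identity is not. A minor unexpected effect of a blood draw, for example, could meet 2.1 without clearly meeting 17.5.

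**Step 3. Is the annual report a different thing from event reporting?** In 17.2 it is: the annual update stands as its own item beside event reporting. In 2.1 the annual basis is attached to the events themselves. That is where the texts conflict.

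**Step 4. Which events are exposed?** Section 2.1 does not exempt serious events, but 11.2.1 and 17.2 give them an explicit route to the IRB. What remains is mainly non-serious unexpected harms and events that change the risk without being serious adverse events.

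**Step 5. Timing.**

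- Time on study, from the synopsis components (screening 1 to 4 weeks, baseline 1, treatment 8, follow-up 4): 1 + 1 + 8 + 4 = 14 weeks at the least and 4 + 1 + 8 + 4 = 17 weeks at the most. This agrees with the 14 weeks in section 4.1 and with the synopsis: "Each subject will be on study for up to 17 weeks".
- Longest wait under an annual rule: 12 months, about 52 weeks.
- Ratio to one participant's time on study: 52/17 = 3.1 and 52/14 = 3.7.
- Average wait if events fall evenly over the reporting year (an assumption): 12/2 = 6 months.
- The longest wait equals the planned one-year recruitment period.

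The delay relative to 17.5 cannot be stated more exactly, because 17.5 does not put a number on prompt.

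**The case against.** The best defence is that 2.1 does not say events are reported *only* once a year. It is narrative in a risk-benefit section and can be read as describing the annual update that 17.2 requires. The binding obligations are in 17.5, which the investigator accepts by signature, and in 17.2 and 11.2.1. An investigator who reported only annually would breach 17.5. There are other channels too: the monthly internal review and contact with the human research protection office in section 14, ongoing monitoring of serious events in the synopsis, and a safety interim analysis when 25% of participants have completed Week 4 (section 15.5).

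Much of this stands as a limit on the size of the problem, and it rules out three stronger readings that a reader might infer.

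- *All safety information could be held back for a year.* The documents do not support this. Only notice to the IRB is in question, and serious events have their own route there.
- *Sections 2.1 and 17.5 cover exactly the same events.* This is not shown, because unanticipated problems are not defined.
- *The IRB would hear only after most participants had finished, or after recruitment had closed.* With even recruitment over 52 weeks and a first report 52 weeks after first enrolment, (52 − 17)/52 = 67% to (52 − 14)/52 = 73% of participants would have finished, about 37 to 40 of 55. But the documents give neither the recruitment pattern nor the start of the annual clock. IRB approval precedes study initiation, so a clock running from approval could bring the first report earlier relative to enrolment.

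The defence does not remove the conflict. The permissive reading of 2.1 has to be supplied by the reader: the sentence has no cross-reference, and no provision ranks the rules. Monthly review with mentors is not notice to the IRB. Contact with the human research protection office is described as regular, but no interval or duty to report individual events is attached to it.

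**Conclusion.** The conflict is real and should be corrected. Section 2.1 assigns annual IRB reporting to events that overlap with those that 17.5 item 8 requires to be reported promptly and that 17.2 sends to the IRB under its own procedures, and the text does not say which provision prevails.

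The consequence is limited. If 2.1 is followed on its own, notice to the IRB could be late by up to about 12 months, roughly 3 to 4 times one participant's time on study. That is a worst case, not an expected delay: it assumes that staff rely on 2.1 alone and that the event falls just after an annual report. It applies mainly to non-serious unexpected harms and risk-changing events.

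This is an internal inconsistency in safety reporting. It has no bearing on the sample size, the endpoints or the analysis. The text of section 11.3 (Medical Monitoring), listed in the table of contents, was not available for this review, so nothing is inferred from its absence. Its wording should be checked when the sections are reconciled.

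**What to change.** Reconcile sections 2.1, 11.2.1, 17.2 and 17.5. Replace the annual-reporting sentence in 2.1 with a cross-reference: unexpected harmful or risk-changing events are reported to the IRB under 17.5 item 8 and 17.2, and serious adverse events also under 11.2.1. Keep the annual report only as a cumulative summary of events already reported, in line with the separate annual update in 17.2. Section 17.2 must be among the references, because it is the section that names unexpected adverse experiences; 11.2.1 covers only serious ones.

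The cost is one sentence, processed as an amendment with IRB approval under 17.1. It creates no duty beyond what 17.5, 17.2 and 11.2.1 already contain. It removes the conflict but does not set a number of days, since none of the three sections gives one. If the sponsor wants a fixed timeline, it can cite the IRB's own policy in the same sentence.
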